6.4.2.3 Laboratory parameters

Laboratory parameters which will be descriptively analyzed are included in Appendix 5. The tabulation of laboratory data will follow in principle the Bayer Global Standard Tables catalogue (currently version 4.0 default), with the necessary modifications like for time interval presentation instead of visit presentation. Treatment-emergent high and low laboratory abnormalities will be summarized by treatment periods (TP1, TP2) and overall.

For immunology and coagulation parameters Intervals 'BL/Post baseline' will be used, while for all other parameters Intervals C will be used (see Figure 4–1). If several laboratory measurements are available for a patient, depending on the laboratory parameter only either the smallest (if small values are considered worse for the parameter) or largest (if large values are considered worse) measurement within Intervals C will be used (see Appendix 5 for details). If both largest and smallest values are specified for a particular parameter, two separate analyses will be done for this parameter, one analysis using the patient's largest measurement across the considered time period and another analysis using the smallest measurement. Both scheduled and unscheduled measurements will be considered.

Central as well as local lab measurements are available. Descriptive statistics will be provided for central lab measurements. Local lab measurements will be listed.

Values below the lower limit of quantification (LLOQ) will be set to LLOQ/2. Values above the upper limit of quantification (ULOQ) will be set to ULOQ.

Estradiol

Absolute values will be analyzed using descriptive statistics by treatment group using Interval C and Interval D (see Figure 4–1). The smallest value (i.e. "worst case") per patient per time interval will be used in the analyses.

The distribution of estradiol values by treatment group using Intervals C and D will be graphically depicted with boxplots. The time course will be shown using line plots depicting the mean and 95% confidence interval (two-sided) and using Intervals C and D as described above. Time intervals including data from less than 10 patients in the respective group will be excluded from the plots.

For estradiol frequency tables with number and percentage of subjects with estradiol (pg/mL) <13, <30 will be displayed by treatment group and Intervals A and B. The subjects with at least one lower value based on each cut-off in any visit during that time interval will be counted.

6.4.2.4 Adverse events

All AEs will be coded by MedDRA terms (the current version at the time of analysis) and classified into pre-treatment AEs, treatment-emergent (TEAE) and post-treatment AEs.

AEs will be flagged as TEAE except for AEs for which there is clear evidence that the AE starts before date of first study drug intake (pre-treatment AEs) or after the date of last study drug intake + 60 days (post-treatment AEs).

AEs with clear evidence of start before the date of first study drug intake are flagged as pretreatment AE unless the AE worsens at or after the date of first study drug intake and before or at the date of last study drug intake + 60 days. AEs starting before but worsening at or after the date of first study drug intake and before or at the date of last study drug intake + 60 days will be considered as two AEs, a pre-treatment AE and a TEAE. The pre-treatment AE will end at the date of worsening and the new TEAE will start at the date of worsening.

Same applies in case an AE starts at or after the date of first study drug intake, but before the date of last study drug intake + 60 days and worsens afterwards, then e.g. leading to a TEAE and a post-treatment AE.

Worsening of an AE is defined as follows:

- AE intensity/grade is worsened (e.g., moderate to severe)
- AE changed to a serious event
- AE ends with death
- AE is drug-related

TEAEs will further be categorized into on-treatment and off-treatment events.

TEAEs will be flagged as on-treatment except for TEAEs where there is clear evidence that the TEAE starts outside all on-treatment phases. Each on-treatment phase starts with the date of first study drug intake and ends with the date of last study drug intake during a treatment period plus 8 days. TEAEs with clear evidence of start outside all on-treatment phases will be flagged as off-treatment TEAEs unless the TEAE worsens during an on-treatment phase. TEAEs starting during off/on-treatment phase, but worsening during an on/off-treatment phase will be considered as two TEAEs, an off/on-treatment TEAE and an on/off-treatment TEAE. The off/on-treatment TEAE will end at the time of worsening and the on/off-treatment TEAE will start at the time of worsening.

Descriptive analysis will be performed (i) by treatment group for both TP1 and TP2 combined, (ii) by treatment group (including pooled treatment group A1+B2) separately for each treatment period and (iii) by study drug for both TP1 and TP2 combined. The tabulation will follow in principle the Bayer Global Standard Tables catalogue (currently V 4.0), with the necessary modifications like for on- and off-treatment TEAEs.

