**Originally, the instructions in Sections 7.1 to 7.4 were the following:**

## **7.1 Treatments to be administered**

Eligible subjects will be randomized to one of the following treatment groups:

A1: vilaprisan (2 mg), 2 treatment periods of 12 weeks, separated by 1 bleeding episode

B1: placebo, 1 treatment period of 12 weeks, and vilaprisan (2 mg), 1 treatment period of 12 weeks, separated by 1 bleeding episode

B2: vilaprisan (2 mg), 1 treatment period of 12 weeks, and placebo, 1 treatment period of 12 weeks, separated by 1 bleeding episode

Randomization will be 1:1:1 and stratified by country/region (US, Japan and other countries) for Treatment Groups A1, B1, and B2.

Each treatment period will consist of 12 weeks (84 days). One tablet (oral) will be taken daily during the treatment periods.

The tablets should be taken at about the same time every day. Exceptions to this rule may occur before visits with PK blood sampling (see Section 9.5.1).

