Taking these aspects into account, a difference in amenorrhea rates of at least 0.4 between vilaprisan 2 mg and placebo is assumed after 12 weeks and 24 weeks. Sample size calculation was further based on a balanced randomization scheme of 1:1:1 (A1:B1:B2), an overall power of 0.9 for the study (ie, higher for each individual test), and the application of the two-sided Cochran–Mantel–Haenszel test for the primary variable and the secondary variable HMB response as well as the logrank test for the secondary variables Onset of amenorrhea and Onset of controlled bleeding (stratified by region/country), each to a local 0.05 significance level.

Assuming a dropout rate of about 20%, the number of subjects to be randomized into the study was planned to be 156 (78, 39, 39 subjects in the US, Japan, other countries, respectively); 52 subjects in each treatment group (26, 13, and 13 subjects in the US, Japan, and other countries, respectively).

Approximately 50% of the subjects were planned to be randomized from the US (based on the feedback from the FDA) and 25% from the subjects were planned to be randomized from Japan and other countries, respectively.

Based upon the anticipated screen failures rates (60% in the US, 30% in Japan, and 50% in other countries), about 329 subjects were planned to be enrolled to achieve the planned number of randomized subjects.

PASS version 13.0.11 was used for sample size calculation.

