Duration	up to120 days		12 weeks	· · · · · · · · · · · · · · · · · · ·	12 weeks	Day 7 to 15 of the 2nd menstrual cycle after EoT

Abbreviations: EoT: End of treatment

The following procedures were implemented prior to the Global Protocol Amendment, version 4.0:

- During the screening period, subjects needed to demonstrate eligibility including the presence of at least 1 uterine fibroid ≥ 30 mm and < 120 mm in largest diameter based on ultrasound, HMB in at least 2 bleeding periods, each with menstrual blood loss (MBL) > 80.00 mL documented by the alkaline hematin (AH) method, and endometrial biopsy results without significant histological disorder.
- Eligible subjects were randomized in 1:1:1 ratio to one of the three treatment groups (A1, B1, or B2) and stratified by country/region (US, Japan and other countries). The time between randomization and start of treatment should not have exceeded 40 days.
- After the end of the final treatment period, subjects were followed up until Day 7 to Day 15 of the 2nd menstrual cycle after end of treatment.

With the implementation of the Global Protocol Amendment, version 4.0, no further subjects were recruited. Patients who were randomized but had not yet started treatment were instructed to not start TP1. Patients already in a treatment period were instructed to complete the current treatment period but to not start a new treatment period. Thus, with the implementation of the Global Protocol Amendment, version 4.0, the originally foreseen study

design outlined in Figure 3–1 is not applicable anymore. With the Integrated Clinical Study Protocol version 5.0 the confirmatory analysis was modified accordingly: The confirmatory analysis (originally including TP1 and TP2) will only be based on results of TP1 as the number of patients who start TP2 is not sufficient for drawing valid conclusions.

All subjects who were randomized and started treatment before the temporary pause were asked to have a comprehensive safety evaluation (with particular focus on endometrial, adrenal and skin safety) performed. This also applies to subjects who have completed or discontinued the study before or during the temporary pause, provided they have taken at least one dose of study medication.

4. General Statistical Considerations

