4.1 General Principles

The statistical analysis will be performed using the software package SAS release 9.4 (SAS Institute Inc., Cary, NC, USA).

The following Bayer standards are applied: RD-OI-0119 'Prepare statistical documents and programs', RD-SOP-1107 'Recording and Evaluation of Bleeding Data' together with corresponding Bayer standard SAS macro BCycle (version 6.0). Furthermore, global standards for tables and data displays are available and will be specified in the tables, listings and figures (TLF) specification document, which will be approved in parallel with this SAP.

All variables will be analyzed by descriptive statistical methods according to their data type. The number of data available, mean, standard deviation (SD), minimum, median and maximum will be calculated for metric data as appropriate. The number of significant digits for minimum and maximum will correspond to that of the original data. The mean and median will be rounded to one more decimal place than the original data, and the SD it will be rounded to two more decimal places than the original data. Frequency tables will be generated for categorical data including percentages with 1 decimal place. In general, the data will be presented by treatment group (see Figure 3–1) or by treatment period within treatment group, and overall, that is, based on the total study population of the respective analysis set. Tables, figures and listings will show the treatment groups, A1, B1 and B2. Additionally, for selected variables the treatment of vilaprisan in TP1 of the treatment groups A1 and B2 will be presented also as pooled.

Variables recorded in the electronic case report form (eCRF) and relevant derived variables will be shown in subject data listings, whereby only randomized patients will be included. Data from screening failures will only be shown in the 'Screening failure' listing.

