6.2.3.4 Ultrasound examination related variables

The following variables will be presented by (pooled) treatment group and by Intervals B as well as by post-baseline visit (i.e. Visit 4, Visit 5, Visit 6, EoT visit, FUP visit, safety closeout visit):

- Percent change in the sum of the volume of the 3 largest fibroids compared to baseline (measured by ultrasound). If less than 3 fibroids are present, the volume of the actual number of fibroids will be summed.
- Percentage change in volume of the largest fibroid from baseline (measured by ultrasound)
- Percent change in volume of uterus compared to baseline (measured by ultrasound)
- Percentage of subjects with a reduction of $\geq 25\%$ of the sum of the volume of the 3 largest fibroids compared to baseline (measured by ultrasound). If less than 3 fibroids are present, the volume of the actual number of fibroids will be summed.
- Percentage of subjects with a volume reduction of ≥ 25% of the largest fibroid compared to baseline (measured by ultrasound)
- Percentage of subjects with a reduction of $\geq 25\%$ of uterine volume compared to baseline (measured by ultrasound)

If multiple volume assessments are available for a time period, the smallest volume measurement will be used for the Baseline time period, and the largest volume measurement will be used for any other time periods of Intervals B.

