6.4.2.12 Bleeding patterns per 28 days and per 84 days based on UF-DBD

The bleeding data recorded on the UF-DBD will be summarized using descriptive statistics in the SAF by treatment groups (including pooled treatment group A1+B2) using Intervals C and D. A reference period of 28 days will be used for most analyses, which corresponds to the Intervals D. When a reference period of 84 days is used, the Intervals D will be modified accordingly.

The bleeding intensity will be summarized by bleeding category using frequency tables by reference period of 28 days and 84 days.

The maximum bleeding intensity will be summarized using frequency tables by 28 days reference period.

The number of bleeding days will be analyzed by 28 days reference period and with the following bleeding categories:

- non-bleeding,
- spotting-only,
- bleeding (bleeding intensity of 'mild' or higher),
- bleeding including spotting (bleeding intensity of 'spotting' or higher),
- mild,
- moderate,
- severe,
- very severe.

An incomplete period which does not comprise 28 (or 84, respectively) days will be analyzed for any of the considered time periods of Intervals C. The analysis of this incomplete period is based on all subjects for whom the length of the considered time period is not a multiple of 28 (or 84, respectively) days. A subject's data from the last x < 28 (x < 84) days of the considered time period will be included.

7. Document history and changes in the planned statistical analysis

The following variables will be analyzed descriptively, even those were not listed as other efficacy/safety variables in the protocol:

- Percentage change in volume of the largest fibroid from baseline (measured by ultrasound)
- Percentage of subjects with a volume reduction of $\geq 25\%$ of the largest fibroid compared to baseline (measured by ultrasound)
- Uterine fibroid surgery performed during the study
- Bleeding patterns per 28 days and per 84 days based on UF-DBD

8. References

- [1] Best practice document RD-SOP-1107: Recording and Evaluation of Bleeding Data. Version 10.0
- [3] Upton GJ. Conditional independence, the Mantel-Haenszel test, and the Yates correction. The American Statistician. 2000 May 1;54(2):112-5.

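### Read literally, two safety sections of the SAP keep the pooled A1+B2 column in Treatment Period 2, when A1 is on vilaprisan and B2 on placebo

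*SAP*

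**What the plan says.** **Treatment sequences (Protocol 7.1).** A1 takes vilaprisan in both periods, and B1 takes placebo first and vilaprisan second. For the remaining group the protocol has "B2: vilaprisan (2 mg), 1 treatment period of 12 weeks, and placebo, 1 treatment period of 12 weeks, separated by 1 bleeding episode". A1 and B2 are therefore identical until TP2 starts and different from then on.

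**General rule (SAP 4.1).** For selected variables, "the treatment of vilaprisan in TP1 of the treatment groups A1 and B2 will be presented also as pooled". SAP 6.2 bases pooling on the two groups having the same treatment and on the gain in power. SAP 6.2.3 repeats the TP1 limit for the further efficacy variables.

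**Default for safety (SAP 6.4).** No pooled A1+B2 results are given unless a section says so.

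**Sections that say so.**
- SAP 6.4.2.4, adverse events: "by treatment group (including pooled treatment group A1+B2) separately for each treatment period". SAP 6.4.2.4.2 applies the same summaries to serious adverse events.
- SAP 6.4.2.12, bleeding patterns: "by treatment groups (including pooled treatment group A1+B2) using Intervals C and D". In Figure 4–1, Intervals C and D both contain TP2 and follow-up.
- SAP 6.2.3.4, ultrasound: "The following variables will be presented by (pooled) treatment group and by Intervals B as well as by post-baseline visit". This section sits under 6.2.3 and its TP1 limit.

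None of these three sections repeats the TP1 limit.

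**The concern.** Pooling is justified only while the two groups take the same drug. There are two treatment periods, so an instruction to show the pooled group for each of them includes TP2. Intervals C and D reach TP2 and follow-up directly. Because the safety default gives way to any section that specifies pooling, a programmer working from 6.4.2.4 or 6.4.2.12 would have grounds to fill the column for every period.

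The TP2 column would then average vilaprisan and placebo subjects under a heading that meant vilaprisan alone one table earlier. Safety is a secondary objective, and these tables carry adverse events, serious adverse events and bleeding patterns. TP2 entry was cut short by the pause, so a reader may be drawn to the larger combined group, which is the column that cannot be interpreted.

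**Working it through.** **1. Planned numbers.** SAP Section 3: "Eligible subjects were randomized in 1:1:1 ratio to one of the three treatment groups". Protocol 10.4: "52 subjects in each treatment group". Check: 3 × 52 = 156, the stated total. Pooled A1+B2 as planned is 52 + 52 = 104.

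**2. Placebo share of the pooled column.** Share s = (pooled subjects on placebo) / (n_A1 + n_B2).
- TP1: 0/104 = 0%.
- TP2 at the planned split: 52/104 = 50%. An equal 20% loss in both groups leaves this unchanged: 41.6/83.2 = 50%.
- TP2 as it happened: SAP Section 3 says too few subjects started TP2 to support conclusions but gives no counts. Assumed A1:B2 entries of 20:10 give 10/30 = 33%, and 10:20 give 20/30 = 67%.

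**3. Effect on a displayed rate.** With rate v on vilaprisan and p on placebo, and no carry-over or period effect assumed, the pooled rate is (1 − s)v + sp. It falls short of the full vilaprisan-minus-placebo difference by s(v − p).

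As an illustration only, take the regional amenorrhea rates from the Phase 2 study ASTEROID 1 in Protocol 10.4 as a stand-in for a bleeding outcome:

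| v / p | pooled, s = 1/3 | pooled, s = 1/2 | pooled, s = 2/3 |
|---|---|---|---|
| 0.7 / 0.2 | 0.53 | 0.45 | 0.37 |
| 0.9 / 0.0 | 0.60 | 0.45 | 0.30 |
| 0.9 / 0.1 | 0.63 | 0.50 | 0.37 |

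At an equal split the column shows 0.45 to 0.50, a value seen on neither treatment.

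**4. Follow-up.** Nobody takes study drug in follow-up, so no placebo share applies; the pooled groups then differ in treatment history. For bleeding patterns the difference is not diluted by subjects who never reached TP2. SAP 4.1 excepts these patterns from the rule that counts such subjects in follow-up for safety variables.

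**5. Do other sections settle it?**
- SAP 4.1 points to TP1 only. SAP 6.4 lets a specific safety section depart from the default, and 6.4.2.4 and 6.4.2.12 are specific. The two readings are not reconciled.
- SAP 6.4.2.2 shows treatment-emergent ovarian-cyst events by TP1, TP2 and overall without naming the pooled group, which it names only for pre- and post-treatment events. The omission in 6.4.2.4 is therefore not house style.
- The by-study-drug adverse-event table covers TP1 and TP2 combined, so it does not supply a clean TP2 aggregate. SAP 6.4.2.12 plans no by-study-drug display.
- For ultrasound, 6.2.3 governs and already limits pooling to TP1.

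**The case against.** The strongest reply is that SAP 4.1 defines the pooled presentation as vilaprisan in TP1, that 6.2.1.1, 6.2.2.1 and 6.2.3 repeat this, and that the later sections use the group name as shorthand for that column. On this reading only a wording gap remains. The column layout is also left to a tables, listings and figures specification approved in parallel, which is not among the documents and may already be right. This reply stands so far as it shows an unresolved conflict rather than a settled intention to pool in TP2. It does not remove the conflict, because the safety default yields to specific sections.

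The replies on consequence also stand. All safety analyses are descriptive. A1, B1 and B2 appear separately. SAP 6.4.2.4.1 assigns each adverse event to a study drug, and a table by study drug is planned.

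Four stronger readings are tempting, and the documents do not support them:
- A reader might infer a reversed treatment comparison in TP2, since B1 is then on vilaprisan and the pooled rate minus the B1 rate would be −s(v − p). No pooled-versus-B1 contrast or test is planned in TP2, and SAP Figure 3–1 shows B1 on vilaprisan there.
- A reader might take the column to be labelled as vilaprisan. The SAP names it only by its groups, A1+B2.
- A reader might extend the one-half placebo share to all later intervals. It applies to TP2 at equal entry. It does not describe follow-up, and the EoT visit includes subjects who never started TP2.
- A reader might count ultrasound as an equal third instance. The limit in 6.2.3 already covers it.

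**Conclusion.** The point holds as an internal conflict with limited reach. Followed literally, SAP 6.4.2.4 (with serious adverse events through 6.4.2.4.2) and 6.4.2.12 yield a TP2 pooled column that mixes two treatments, and 6.4.2.12 also yields a follow-up column that mixes two treatment histories. Both contradict the TP1 limit in 4.1 and the reason for pooling in 6.2. The TP2 placebo share is 50% under equal entry and 33% to 67% over the assumed range; the true share cannot be derived from the documents. The amenorrhea figures illustrate the mixing and do not predict any planned table. The confirmatory TP1 comparison of pooled A1+B2 with B1 is correct and unaffected. Ultrasound needs a clarification only.

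**What to change.** - **SAP 6.4.2.4 (and through it serious adverse events) and 6.4.2.12:** state that pooled A1+B2 is shown only for data before TP2 starts, meaning baseline, TP1 and the treatment break, and that from TP2 start A1, B1 and B2 are shown separately. Keep the break in the pooled column, because A1 and B2 still share the same treatment history there and 6.4.2.4.1 assigns events before TP2 to the TP1 drug.
- **SAP 6.2.3.4:** repeat the TP1 limit from 6.2.3 as a clarification. Intervals B join TP1 and the break, so name that combined interval as the one that may carry the pooled column.
- **Tables, listings and figures specification:** check that the column headings follow the same rule.

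The cost is a few sentences and fewer columns. Nothing interpretable is lost, because the separate group columns remain and the valid pooled summary of the break is kept.

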### **10.3.2.4 Safety analysis**

Safety analyses will be performed on the SAF. AEs and other safety variables will be summarized descriptively by treatment group.

The incidence of treatment-emergent AEs and drug-related AEs will be summarized using MedDRA preferred term and the primary system organ class.

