6.4.2.4.1 Assignment to study drug

Depending on the TEAE onset, the AE will be assigned to a study drug. This is relevant for subjects with switch in study drug (i.e., treatment groups B1 and B2), as it may not be clear whether the TEAE is assigned to the study drug given in TP1 or to the study drug given in TP2.

- AEs with an onset before the start of TP2 will be assigned to the study drug given in TP1.
- AEs with an onset at or after the start of TP2 will be assigned to the study drug taken during TP2.

Consequently, AEs with an onset before start of TP2 which are ongoing during TP2 will not be assigned to the study drug given in TP2 unless the TEAE worsens after start of TP2. In case it is not clear to which study drug the AE will be assigned (for example, due to partially missing dates), those AEs will be assigned to vilaprisan (conservative approach).

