AESIs based on investigator assessment and AESIs based on MedDRA groupings will be presented separately. They will be presented by AESI group (if available), MedDRA primary SOC and PT and study drug. Summary tables for AESIs by maximum intensity and by worst outcome will be produced. Furthermore, listings will be provided.

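### By-study-drug adverse-event tables name no person-time, and the AESI text does not say that the TP1 comparison also applies, although time at risk per woman is longer on vilaprisan

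*SAP*

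**What the plan says.** **Sequences.** Protocol 7.1 randomises 1:1:1 to three groups. Only the first is planned to repeat a drug: "A1: vilaprisan (2 mg), 2 treatment periods of 12 weeks, separated by 1 bleeding episode". In B1, placebo comes first and vilaprisan second. B2 reverses that order, so women in these two groups have at most one course of each drug.

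**Layouts.** SAP 6.4.2.4 gives three for adverse events: by group over both periods, by group within each period (with A1 and B2 also pooled), and "iii) by study drug for both TP1 and TP2 combined". For AESIs, SAP 6.4.2.4.2 says: "They will be presented by AESI group (if available), MedDRA primary SOC and PT and study drug". In the same section, SAEs are given the TEAE layouts. In SAP 6.4.2.2, ovarian-cyst events are given by-group tables for TP1, TP2 and overall, with study drug as an addition. The AESI text has neither form of words.

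**Attribution.** Under SAP 6.4.2.4.1, "AEs with an onset before the start of TP2 will be assigned to the study drug given in TP1". Later events go to the TP2 drug, and events with unclear assignment go to vilaprisan.

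**Measure.** Protocol 10.3.2.4: "The incidence of treatment-emergent AEs and drug-related AEs will be summarized using MedDRA preferred term and the primary system organ class". Neither document names an exposure-adjusted adverse-event rate. SAP 6.1.6 summarises exposure by study drug, but separately from the event counts.

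**The concern.** In a by-study-drug table, a woman in A1 who starts TP2 has her whole event window counted as vilaprisan: both courses, the break and the tail. A woman in B1 or B2 who starts TP2 has her window split between the drugs. A percentage of women with an event ignores this difference, so equal risks on the two drugs would appear as an excess on vilaprisan. Sending unclear onsets to vilaprisan pushes the same way.

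This matters most for AESIs. They include the endometrial, adrenal and skin events for which the safety follow-up was set up, and the AESI text names study drug as its comparative layout without mentioning the by-period one. If it is programmed literally, the AESI tables would lack the comparison in which planned exposure is balanced.

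**Working it through.** The plan states no person-time or event rate by drug, so there is no figure to reproduce. The planned size is 3 × 52 = 156 (Protocol 10.4).

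**Inputs from the documents**
- Equal groups of 52. The group size cancels from the ratio.
- Period length 84 days (Protocol 7.1).
- TEAE window to last dose plus t = 60 days (SAP 6.4.2.4).
- Attribution to the TP1 drug until TP2 starts, then to the TP2 drug (SAP 6.4.2.4.1).

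**Assumptions**
- Share f starting TP2: not given, taken from 0 to 1 and the same in each group.
- Break b: 28 days, with 49 days also tried.
- No early discontinuation.
- The same constant hazard λ on both drugs.

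**Step 1: time at risk, in days per 52 women**

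Vilaprisan:
- A1: (1−f)(84+t) + f(168+b+t)
- B1: f(84+t)
- B2: (1−f)(84+t) + f(84+b)
- Sum: 2(84+t) + 2f(84+b)

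Placebo:
- B1: (1−f)(84+t) + f(84+b)
- B2: f(84+t)
- Sum: (84+t) + f(84+b)

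Total vilaprisan time is exactly twice placebo time. The women exposed number 2+f against 1+f groups of 52. The ratio of mean time per woman is therefore 2(1+f)/(2+f), whatever b and t are. The on-treatment window (84+8 days per course) gives the same ratio.

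**Step 2: planned design, f = 1**

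Vilaprisan has 208 courses in 156 women; placebo has 104 courses in 104 women. In days, (256+144+112)/3 = 170.7 against (112+144)/2 = 128.0, ratio 1.33.

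**Step 3: crude incidence with no drug effect**

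Incidence is the mean of 1−exp(−λT) over exposed women, with λ = −ln(1−r)/84 and r the 12-week risk. With r = 5% and b = 28:

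| f | Women, vilaprisan / placebo | Mean days | Time ratio | Crude incidence | Incidence ratio |
|---|---|---|---|---|---|
| 1 | 156 / 104 | 170.7 / 128.0 | 1.33 | 9.8% / 7.5% | 1.31 |
| 0.5 | 130 / 78 | 160.0 / 133.3 | 1.20 | 9.3% / 7.8% | 1.19 |
| 0.25 | 117 / 65 | 152.9 / 137.6 | 1.11 | 8.9% / 8.1% | 1.10 |
| 0 | 104 / 52 | 144.0 / 144.0 | 1.00 | 8.4% / 8.4% | 1.00 |

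At f = 1 the incidence ratio is 1.33 for r = 1% and 1.24 for r = 20%. At f = 0.25 it is 1.11 and 1.08.

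**Step 4: after the change**

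First events divided by woman-time at risk estimate λ on both drugs, so the ratio is 1.00 for every f. TP1 alone (A1+B2 against B1) has equal planned exposure per woman and also gives about 1.00.

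**The case against.** **A reader might infer that study drug is the only layout planned for AESIs.** The documents do not settle this. AESIs are adverse events, the three layouts stand in the parent section, SAP 4.1 makes treatment group or period within group the default, and Protocol 10.3.2.4 summarises adverse events by treatment group. The AESI sentence does not say that it excludes these. What stands is an ambiguity: the text for SAEs and cyst events spells out the wider layouts, and the AESI text does not.

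**A reader might infer that a true excess could not be separated from longer exposure.** That goes too far. The SAP analyses several of the same domains in ways that partly separate exposure:
- laboratory abnormalities by period (6.4.2.3) and Kaplan-Meier estimates for ALT (6.4.2.8);
- endometrial histology and thickness by interval and by treatment duration (6.4.1.1, 6.4.1.2);
- bleeding patterns by interval (6.4.2.12);
- skin findings by treatment group (6.4.2.11).

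**The constant-hazard model does not fit every AESI.** Adrenal and skin findings come largely from one closeout screen, introduced in November 2019 after a pause that began in December 2018. Most would fall beyond last dose plus 60 days, so a rate over the treatment-emergent window would treat a screening prevalence as an incidence. Heavy bleeding is expected to return after treatment (Protocol 9.6.3.2.7), so its hazard is not constant either. This objection stands, and it limits both the sizes above and the remedy.

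**The effect may be small.** SAP section 3 says too few women start TP2 for valid conclusions. With f = 0.25, full planned enrolment and a 2% 12-week risk, crude incidence is about 3.6% against 3.3%. That is about 0.2 of a woman among 65 on placebo, where the standard error is √(0.033 × 0.967/65) ≈ 2.2 percentage points. The tilt also runs against vilaprisan, so it does not hide a signal.

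Finally, the table catalogue and the TLF specification were not available. The absence of person-time is inferred from the SAP and protocol text.

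**Conclusion.** The point holds as a gap in specification with a known direction. For treatment-emergent events, crude by-drug incidence overstates vilaprisan relative to placebo under equal hazards whenever any A1 woman started TP2. The time-at-risk ratio is 2(1+f)/(2+f), assuming equal groups, a common f and no early discontinuation. The figure 1.33 is the ceiling of the planned design and should not be read as the expected size: f is not given, and the pause points to the lower values. For rare events the incidence ratio is close to the time ratio; for common events it is smaller.

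All safety analyses are descriptive (SAP 6.4), so no test or success criterion is affected. The change is still worth making, because the AESI text followed literally gives a contrast that is tilted under no drug effect, and the data needed to remove the tilt are already held.

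**What to change.** 1. In SAP 6.4.2.4.2, state that treatment-emergent AESIs are also tabulated for TP1 by treatment group, pooled A1+B2 against B1, using the second layout of 6.4.2.4.
2. In the by-study-drug TEAE, SAE and treatment-emergent AESI tables, add woman-time at risk and the exposure-adjusted rate: women with a first event per 100 woman-years, using the assignment windows of 6.4.2.4.1 for the denominator.
3. Do not apply these rates to adrenal and skin findings from the closeout screen, or to other AESIs starting after last dose plus 60 days. Show these separately as proportions of women examined, by treatment group or by whether and how long the women received vilaprisan. SAP 6.4.2.10 already takes closeout attendees as its denominator for adrenal tables.

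The cost is SAP and TLF wording, a few columns and one or two tables from data already collected. The only downside is slightly longer tables.
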